6.9.2. Laboratory Assessment and Destruction of Human Biological Samples

All samples will be analysed at the end of study as per standard operating procedures and validated techniques / methods. All protocol required laboratory assessments, must be conducted in accordance with the Laboratory Manual or according to the laboratory section of the Protocol, and Protocol Schedule of Events.

~~Post laboratory assessment, all samples will be stored in requisite storage conditions mentioned for respective samples and will be destroyed within one year after last participant last visit.~~ No biological samples should be destroyed without a prior written agreement between GSKCH and the study centres.

6.10. Dietary Counselling

Dietary counselling sessions will be administered at school. It will be administered to all study participants and their parents/LARs. It is preferable that both parents of participants are provided dietary counseling, but in case if it is not possible then either of mother or father will be provided dietary counselling. Separate sessions of dietary counseling will be held for participants and parents/LARs. Attendance by the school teachers will be strongly encouraged. Study dieticians will administer, supervise and ensure delivery of counselling as per the schedule.

A total of 7, separate sessions for study participants and parents/LAR as described in table below:

Session No	Nutritional Educational Counselling	Duration (in min)
Session 1	Delivery of contents	60 + up to 10 min
Session 2		60 + up to 10 min
Session 3	Follow up of contents delivered in Session 1 and 2: Reinforcement and Problem Solving	30 + up to 10 min
Session 4		30 + up to 10 min
Session 5		30 + up to 10 min

 GlaxoSmithKline	Document Name	Clinical Study Protocol 204477		
	Type	Version	Document Identifier	Effective Date
	eldo_clinical_doc	5.0; Most-Recent; Effective; CURRENT	090032d580daa95e	10-Oct-2017 06:16:49
	Reason For Issue	Auto Issue		

Session 6		30 + up to 10 min
Session 7		30 + up to 10 min

Counseling will be provided by dietician/nutritionist, well versed with local language and with effective education and counseling skills. Contents of the dietary counseling will be socio-culturally acceptable and explained in the language participants, parents and teachers can understand. Contents of dietary counseling will be based on the Dietary Guidelines for Indians, established by the Indian Council of Medical Research (National Institute of Nutrition), and will be provided as per Appendix 8. Study dietician/nutritionist will be instructed to cover each topic described under each session, adequately so as to finish the session within the stipulated time. Start time and end time of each session will be captured in eCRF.

Each session will be followed by up to 10 min of question-answer session. Respectful, science-based answers to participants' questions will be delivered.

Each participant/parent (either of mother or father)/LAR is required to attend all dietary counseling sessions on 'delivery of contents' (i.e. session number 1 & 2) and minimum of three out of five 'follow up' dietary counselling sessions (i.e. session number 3, 4, 5, 6 & 7). Participant will be considered as non-compliant if the participant/parent/LAR does not attend either of session number 1 & 2 OR three or more sessions out of session number 3, 4, 5, 6 & 7.

In case, if any dietary counselling session is not conducted due to reasons such as school exams, long school holidays etc, the next session for dietary counseling will be postponed and conducted as soon as participant is available in school and exams are finished. However, last dietary counselling session (i.e. session no 7), in any scenario, will not be conducted any later than the last day of 8th month of intervention period of a particular subject. A minimum of 4 weeks of gap between consecutive content delivery session and follow up session (i.e. between session 2 and 3); and two consecutive follow up dietary counselling sessions (i.e. between session 2, 3, 4, 5, 6 and 7) must be maintained.

6.11. Clinical Outcomes Assessment

6.11.1. Case/Illness definition

For the purpose of study, GI and respiratory illnesses will be evaluated. These study illnesses are defined as follows:

 GlaxoSmithKline	Document Name	Clinical Study Protocol 204477		
	Type	Version	Document Identifier	Effective Date
	eldo_clinical_doc	5.0; Most-Recent; Effective; CURRENT	090032d580daa95e	10-Oct-2017 06:16:49
	Reason For Issue	Auto Issue		

- A. **GI illness:** An acute illness that includes any of following symptoms: 3 or more loose/liquid/watery stools and/or any vomiting in 24 hours [WHO, 2016] [Azor-Martinez E *et al*, 2014].

Diarrhea, vomiting arising due to non-infectious causes, such as Irritable Bowel Syndrome (IBS), and medications will be excluded from the diagnosis.

- B. **Respiratory illness:** An acute illness that included ≥ 1 of the following symptoms: runny nose, stuffy or blocked nose, cough, fever or chills, sore throat, or sneezing [Sandora *et al*. 2016].

Symptoms arising due to non-infectious causes (e.g., allergy) will be excluded from the diagnosis.

6.11.2. Morbidity Outcomes Definitions

Following morbidity outcomes with respect to GI and respiratory illnesses are going to be evaluated in the study:

- A. **Number of illness days:** Number of days a participant is ill because of GI and/or respiratory illnesses as diagnosed by study physician, as per the criteria defined, over the intervention duration. This corresponds to total number of days (symptomatic or asymptomatic) in an episode of illness.
- B. **Frequency of illnesses:** Total number of illness episodes of GI and/or respiratory illnesses, divided by duration of intervention, where each episode is defined as each incidence of illness followed by at least 3 symptom free days [Azor-Martínez *et al.*, 2014] [Barreto ML *et al.*, 1994] [Sur D *et al.*, 2003].

For the purpose of study, each occurrence of an illness is defined as an event which incorporates a period which includes all illness days uninterrupted by any symptom free day. Thus, an episode may consist of one or more than one occurrences of illness.

- C. **Severity of an illness episode:** Intensity of GI and/or respiratory illnesses; **WILL BE EVALUATED AND CLASSIFIED AS PER CRITERIA SPECIFIED IN APPENDIX-5 (BASED ON CTCAE 2010)** ~~which is evaluated and classified as follows:~~

- ~~➤ Severity of GI illnesses [CTCAE 2010]~~
- ~~a. Diarrhoea:~~

 GlaxoSmithKline	Document Name	Clinical Study Protocol 204477		
	Type	Version	Document Identifier	Effective Date
	eldo_clinical_doc	5.0; Most-Recent; Effective; CURRENT	090032d580daa95e	10-Oct-2017 06:16:49
	Reason For Issue	Auto Issue		

- ~~Mild, ≤ 3 loose stools/day~~
- ~~Moderate, 4 to 6 loose stools/day~~
- ~~Severe, ≥ 7 loose stools/day~~

~~b. Vomiting:-~~

- ~~Mild, 1 to 2 bouts/day~~
- ~~Moderate, 3 to 5 bouts/day~~
- ~~Severe, ≥ 6 bouts/day~~

~~➤ Severity of respiratory illnesses~~

- ~~Mild Easily tolerated, causing minimal discomfort and not interfering with normal everyday activities.~~
- ~~Moderate Sufficiently discomforting to interfere with normal everyday activities.~~
- ~~Severe Any event that prevents normal everyday activities.~~

D. School absenteeism: Number of days when a child fails to attend school because of GI and/or respiratory illnesses.

6.11.3. Clinical Evaluation Tools

A. Parent/LAR reported Symptom Checklist

At the beginning of the study, parents/LARs will be provided with blank ‘symptom checklist’ forms. The symptom checklist to be used by the parents/LARs has been appended (Appendix 3). When a symptom is observed in the participant during the intervention period, the parents will be required to fill the symptom checklist as trained by study staff. The severity/intensity of severity assessment of the symptoms e.g. sore throat, dry cough, wet cough, runny nose, stuffy/blocked nose and sneezing will be made by parents/LARs as per the following criteria:

- Mild – Easily tolerated, causing minimal discomfort and not interfering with normal everyday activities.
- Moderate – Sufficiently discomforting to interfere with normal everyday activities.
- Severe – Any event that prevents normal everyday activities.

Parents/LARs will be trained by study staff to assess the symptoms based on above criteria. For the assessment of other symptoms e.g. diarrhea/loose stools, vomiting and fever, the criteria are already mentioned in the symptom checklist which are in

	Document Name	Clinical Study Protocol 204477		
	Type	Version	Document Identifier	Effective Date
	eldo_clinical_doc	5.0; Most-Recent; Effective; CURRENT	090032d580daa95e	10-Oct-2017 06:16:49
	Reason For Issue	Auto Issue		

line with assessment done as per CTCAE 2010. Parents/LARs will also be provided with digital thermometers to check temperature in case if fever is observed.

In cases where parents/LARs do not observe any symptoms in the participant, they will be asked to mark the relevant ('No') box mentioned for each symptom for each day in the symptom checklist. The symptom checklist will be handed to study physician on weekly basis for review by physician. The physician will then evaluate the symptoms, if any, to determine diagnosis.

Those requiring hospitalisation or specialised care will be referred to the secondary or tertiary care hospital, as deemed necessary by the study physician. The determined diagnosis will be captured in the CRF, and the severity will be graded based on the criterion indicated in Appendix 5.

B. Diagnosis Form

Diagnosis form (DF) will be used to note the diagnosis, severity and school absenteeism due to GI and respiratory illnesses only, as defined in the study protocol. DF will also be used to capture start and end date of all occurrences of GI and respiratory illnesses in the week.

Other morbidity outcomes such as number of illness days, number of episodes, frequency due to GI and respiratory illnesses, as defined in the study protocol, will be calculated programmatically using statistical analysis software (SAS).

Data on diagnosis and morbidity outcomes by study physician on the DF will be used for analysis. DF will be filled as per the details obtained from:

- Symptom checklist filled by parents/LARs
- External clinical record, if treated by an external physician
- Direct information by participants/parents/LARs
- Clinical history and examination by study physician

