6.12.1. Collection of Symptom Checklist

Parent/LAR-reported symptom checklist will be collected on each weekly review. Physician will review the parent/LAR Symptom checklist and conduct clinical examination of only those participants who present with symptoms on the symptom checklist or inform the physician directly.

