12.3. Appendix 3 - Parent/LAR reported Symptom Checklist

Screening Number _____ Week: From ___/___/___
 To ___/___/___

Dear Parent/LAR,

Please report to study staff any other symptoms not listed below.

Please use DD/MM/YYYY format for entering dates.

Please use the following guidelines to grade intensity-

¹Mild – easily tolerated, causing minimal discomfort and not interfering with normal everyday activities.

²Moderate – sufficiently discomforting to interfere with normal everyday activities.

³Severe – any event that prevents normal everyday activities.

Symptom	Date	Yes	No	No of loose stools passed in a day		
				3	4-6	≥7
Diarrhea/ Loose stool	___/___/___					
	___/___/___					
	___/___/___					
	___/___/___					
	___/___/___					
	___/___/___					
	___/___/___					
Symptom	Date	Yes	No	No of bouts in a day		
Vomiting	___/___/___					
	___/___/___					
	___/___/___					
	___/___/___					
	___/___/___					

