12.5. Appendix 5 - Diagnosis Form (DF)

Screening Number _____ **Week: From** ___/___/___
To ___/___/___

1. Was a parent/LAR symptom checklist received for this week? Yes/No
2. Did the subject inform the study physician directly of any Symptoms? Yes/No
3. If any symptoms were confirmed, was a diagnosis for GI and respiratory illnesses provided by the study physician? Yes/No/Not applicable

Note:

- a) If applicable, fill out the following diagnosis chart
- b) No. of ill days will be calculated programmatically for GI and respiratory illnesses reported in the study.
- c) School absenteeism in the DF will be marked for absenteeism due to GI and respiratory illnesses only.
- d) Number of episodes of illness for a particular week will be determined programmatically.
- e) Parents/LAR will also be asked to report to the study physician/study staff any other symptoms observed in participants but are not listed parent/LAR symptom checklist and will be entered in the AE forms.

GlaxoSmithKline

Document Name	Clinical Study Protocol 204477		
Type	Version	Document Identifier	Effective Date
eldo_clinical_doc	5.0; Most-Recent; Effective; CURRENT	090032d580daa95e	10-Oct-2017 06:16:49
Reason For Issue	Auto Issue		

Diagnosis Occurrences in this week	GI Illnesses (Yes  No )		Respiratory Illnesses (Yes  No )
	Diarrhea 	Vomiting 	
First Occurrence			
AE Report Number (from paper AE form)			
Start Date			
End Date			
Severity	 Mild  Moderate  Severe	 Mild  Moderate  Severe	 Mild  Moderate  Severe
School absenteeism (No. of days in this week)			
AE Number (from eCRF)			
Second Occurrence			
AE Report Number (from paper AE form)			
Start Date			
End Date			
Severity	 Mild  Moderate  Severe	 Mild  Moderate  Severe	 Mild  Moderate  Severe
School absenteeism ¹ (No. of days in this week)			
AE Number (from eCRF)			
Third Occurrence			
AE Report Number (from paper AE form)			
Start Date			
End Date			

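### A blocked nose alone counts as a respiratory illness, but the parent checklist has no entry for it, so days with no other symptom may be missed from the primary endpoint

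*Protocol*

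**What the plan says.** Protocol Section 6.11.1 defines a respiratory illness as an acute illness with at least one of "runny nose, stuffy or blocked nose, cough, fever or chills, sore throat, or sneezing", excluding non-infectious causes. One of these is enough.

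Section 6.11.3 names Appendix 3 as the parents' checklist and says that the assessment, as mild, moderate or severe, of "sore throat, dry cough, wet cough, runny nose, stuffy/blocked nose and sneezing will be made by parents/LARs". When no symptom is seen, parents mark No for each listed symptom on each day.

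Appendix 3 opens with the instruction "Please report to study staff any other symptoms not listed below". Appendix 5, note (e), repeats this and gives the destination: parents are asked to report "any other symptoms observed in participants but are not listed parent/LAR symptom checklist and will be entered in the AE forms".

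Two further rules decide what happens next. Under Section 6.12.1 the weekly review involves "examination of only those participants who present with symptoms on the symptom checklist or inform the physician directly". On the data source, Section 6.11.3 states: "Data on diagnosis and morbidity outcomes by study physician on the DF will be used for analysis". SAP Section 4.4.1.1 likewise works from the dates on the Diagnosis Form.

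**The concern.** The instrument does not match the endpoint definition. A symptom that is sufficient for a case, and that the text says is graded daily, has no place on the form used for daily recording. The one written instruction for unlisted symptoms leads to a different form from the one that is analysed.

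The primary endpoint is a count of days built from start and end dates, so completeness of daily capture matters. The planned contrast is small: 7.0 − 6.3 = 0.7 days per child over nine months (Section 9.1). The trial is open label, and contact with staff differs by arm: on school days test children take two supervised doses (Section 5.3), while controls receive no product. Capture that relies on unprompted or unstructured reporting could therefore differ between arms, in a direction that cannot be fixed in advance.

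**Working it through.** No stated figure is in dispute, so the check sets the passages side by side and then applies the SAP's counting rule.

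**1. Symptom lists compared**

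| Respiratory symptom in 6.11.1 | Assessed by parents per 6.11.3 | Block in Appendix 3 |
|---|---|---|
| Runny nose | yes | yes |
| Stuffy or blocked nose | yes | **none** |
| Cough | yes (dry, wet) | yes (dry, wet) |
| Fever or chills | fever | fever; no separate entry for chills |
| Sore throat | yes | yes |
| Sneezing | yes | yes |

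With diarrhoea and vomiting, Appendix 3 has eight blocks. There is no free-text row. A block lost in the conversion from PDF is unlikely: each block has its seven date rows, runny nose is followed directly by sneezing, and sneezing by the signature line. (The column sub-headings for vomiting are missing from the converted text.)

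**2. A week in which a blocked nose is the only symptom**

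- Every listed symptom is truthfully marked No. The form then shows a symptom-free week, not missing data.
- Section 6.12.1 requires no examination unless someone tells the physician directly.
- If the parent tells study staff, note (e) directs the entry to the AE forms. Neither document states a rule that carries a 6.11.1 symptom from there to the Diagnosis Form.

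**3. Effect on the count**

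SAP Section 4.4.1.1 takes asymptomatic days = (second start date − first end date) − 1. Fewer than 3 means one episode, with the gap counted as ill days; 3 or more means two episodes. The cases below are invented to show the rule, and assume that Diagnosis Form dates follow the checklist and no other route catches the days.

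| Course of illness | By definition | From the checklist alone |
|---|---|---|
| Blocked nose only, 3 days | 3 days, 1 episode | 0 days, 0 episodes |
| Runny nose Mon–Tue, blocked nose only Wed–Thu | 4 days, 1 episode | 2 days, 1 episode |
| Runny nose Mon, blocked only Tue–Wed, sneezing Thu | 4 days, 1 episode | (Thu − Mon) − 1 = 2, so 4 days, 1 episode |
| Runny nose Mon, blocked only Tue–Thu, sneezing Fri | 5 days, 1 episode | (Fri − Mon) − 1 = 3, so 1 + 1 = 2 days, 2 episodes |

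Loss is confined to isolated episodes, leading or trailing days, and internal gaps of 3 days or more. Shorter internal gaps are bridged. The last case also raises the episode count, which feeds a secondary endpoint.

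**4. Size**

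Neither document gives the share of ill days on which a blocked nose is the only symptom, nor the share of these that other routes would catch. No estimate follows.

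**The case against.** The strongest case against is that the checklist is only one of several ways in.

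- Section 7.4 requires staff to ask at each visit whether the child has felt unwell or had any symptoms, and the Schedule of Events places AE monitoring at the weekly reviews. Symptoms off the checklist are therefore asked about in both arms.
- Section 6.11.3 lets the Diagnosis Form be filled from outside clinical records, direct information, and the physician's history and examination as well as the checklist. The form itself asks whether the child told the physician of symptoms.
- Section 6.12.2 places a physician at school on all school days.
- Each occurrence on the Diagnosis Form has fields for AE numbers, so the two records are meant to coexist.

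All of this stands. It rules out two stronger readings that a reader might infer: that blocked-nose days are recorded only if a parent volunteers them, and that entry on an AE form takes them out of the endpoint. The documents say neither.

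It does not close the gap. The Section 7.4 question is general, and what it elicits is directed to the AE section of the CRF. When a weekly review is missed, Section 6.12 asks only for the checklist to be collected by telephone or home visit. For illness away from school, the checklist is the prescribed tool. These routes are less structured than a daily yes/no entry, and they lack the rule that would make them complete.

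**Conclusion.** The inconsistency is real and should be corrected. Section 6.11.3 describes a checklist that Appendix 3 does not provide, and note (e) leaves it unstated whether a qualifying symptom reported outside the checklist is assessed for the Diagnosis Form. Days with a blocked nose as the only symptom may be under-recorded in the ways shown, and this could differ by arm. Loss is possible, not automatic, and the range of days at risk is narrow.

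A reader might go on to assume a percentage of ill days lost and derive a fall in power. The documents do not support that. They give no such percentage, and the planning mean of 7 days was built from years-lost-to-disability data for diarrhoea, lower respiratory infection, other infectious disease and nutritional deficiency (Section 9.1). Nothing shows that it contains blocked-nose-only days to lose. The conclusion rests on the forms being used as written; site training may already cover the symptom, but the documents do not say so.

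**What to change.** - Add a stuffy/blocked nose block to Appendix 3, in the same layout as the other nasal symptoms: seven dates, yes/no, and mild/moderate/severe. Add any matching CRF entry.
- State in Appendix 5 note (e) that any symptom named in Section 6.11.1, however it is reported, is assessed for the Diagnosis Form as well as for any AE entry. This sentence also covers chills.
- Bring both changes in on the same date in all schools and record that date. Do not ask again about past weeks: recall would be unreliable and, in an open-label trial, could itself differ by arm.

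The cost is one form block, one sentence, a CRF update and brief retraining of parents. Classification should follow the sponsor's own amendment process. That process lists changes to assessment variables among major amendments, while Amendment 8, which aligned severity grading between Section 6.11.2 and Appendix 5, was handled as minor.

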6.12. Study Physician Weekly Review

To ensure that no case is missed, a weekly review (SPWR) will be scheduled by the study physician to check symptom checklist from all participants.

 GlaxoSmithKline	Document Name	Clinical Study Protocol 204477		
	Type	Version	Document Identifier	Effective Date
	eldo_clinical_doc	5.0; Most-Recent; Effective; CURRENT	090032d580daa95e	10-Oct-2017 06:16:49
	Reason For Issue	Auto Issue		

SPWR will initiate 1 week (+up to 2 days) post first dietary counselling visit of the participant and will continue on a weekly basis (+ up to 2 days) until end of study visit. ~~At least one weekly review with the study physician will occur after product administration stops~~ **LAST SPWR WILL BE CONDUCTED ON END OF STUDY VISIT DAY, EVEN IF SYMPTOMS ARE ASSESSED FOR LESS THAN A WEEK IN SYMPTOM CHECKLIST FORM.**

In case the SPWR of a participant is not conducted due to reasons such as absenteeism, long holidays etc for a week, then every attempt will be made to contact and collect symptom checklist from participant/parents/LARs, either telephonically or visiting them at home. If any participant is not accessible for consecutive 4 weeks, he/she will be considered as lost to follow up.

6.12.1. Collection of Symptom Checklist

Parent/LAR-reported symptom checklist will be collected on each weekly review. Physician will review the parent/LAR Symptom checklist and conduct clinical examination of only those participants who present with symptoms on the symptom checklist or inform the physician directly.

6.12.2. Study Physician Clinical History and Examination

Study physician will be made available at school on all school days during school timings.

When the participant **falls sick at school** during school timings with the pre-specified symptoms related to GI and respiratory illnesses, participant will be presented to the study physician. Study physician will collect relevant clinical history from participants and parents/LARs (if available). Study physician will systematically evaluate the symptoms using well-defined, pre-established criteria and will make objective diagnosis of the clinical outcomes, as defined in the study protocol.

When study participant **fall sick but are not at school** (e.g. during holidays, after school dismissal etc), with the pre-specified symptoms related to GI and respiratory illnesses, parents/LARs would need to complete the 'symptom checklist' provided to them. Symptom checklist would be presented to study physician by the participants/parents/ LARs. In case, if an external physician is consulted for the treatment, clinical record form from the same would also be presented to the study physician along with symptom checklist. Study physician will collect relevant clinical history from participants and parents/LARs (if available). Study physician will evaluate and verify parent reported data on symptom checklist and clinical record form from external

 GlaxoSmithKline	Document Name	Clinical Study Protocol 204477		
	Type	Version	Document Identifier	Effective Date
	eldo_clinical_doc	5.0; Most-Recent; Effective; CURRENT	090032d580daa95e	10-Oct-2017 06:16:49
	Reason For Issue	Auto Issue		

physician. Study physician will systematically evaluate the symptoms (if still present in the participants) using well-defined, pre-established criteria and will make objective diagnosis of the clinical outcomes, as defined in the study protocol.

Diagnosis by study physician on DF will be used for analysis. In case of a conflict between parent-reported symptoms, external physician's reported diagnosis and study physician's diagnosis, the study physician's diagnosis will supersede.

Availability of physician will also ensure the children are provided with timely care, which could include the advice to use a hydration formula and/or medications (*e.g.*, antibiotic, nasal decongestant) to help manage their symptoms/infection. If and when needed, and, if possible, the same type of hydration formulas and medications would be provided to children – *e.g.*, the same type of antibiotic, the same type of nasal decongestant, *etc.*

6.13. 24 hr Dietary Recall & Dietary Diversity Survey

6.13.1. 24 hr Dietary Recall

This method involves a structured interview and will be conducted as per the questionnaire provided in Appendix 6. Since children, invariably tend to overestimate, parents/LARs should be present at the 24-hour recalls. Majority of the information should come from the parent/LARs, with the child making additions to fill in the gaps.

Respondents (participant/ Parents/LARs) will also be asked whether or not the day recalled is typical of their usual food consumption, or if it was unusual or restricted in any way *e.g.* fast, festival *etc.* If the day is not the representative of a typical day then the participant may be called for another day.

On confirmation of the day being a representative of a typical day, a trained study staff will ask the respondents (participant/ parents/LARs) to recall all food and beverage consumed by the child during previous 24 hours. For homemade food and beverage, following information will be recorded:

- List of ingredients: *e.g.* water, oil, herbs, spices.
- Amounts of ingredients: This can be in household measures, weights or using portion sizes.
- Cooking method: Record some brief information on how the dish was prepared and cooked.

 GlaxoSmithKline	Document Name	Clinical Study Protocol 204477		
	Type	Version	Document Identifier	Effective Date
	eldo_clinical_doc	5.0; Most-Recent; Effective; CURRENT	090032d580daa95e	10-Oct-2017 06:16:49
	Reason For Issue	Auto Issue		

The food or beverage items which are bought, name of the brand will be enquired. A portion size can be described in terms of either household measures (e.g. one level teaspoon of sugar, bowl, cup etc) or weights.

Calculation on energy and the macronutrients (protein, carbohydrates and fat) will be made using application/software. For the purpose latest available Dietsoft software available at <http://dietsoft.in/> based on Indian data (NIN and ICMR) will be used.

